## Research Summary

### State your primary study objectives

Evaluate the acceptability, feasibility, and fidelity of current Vivo prototype in sedentary older adults with prediabetes.

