## Standard Research Summary

### Purpose of the Study

- Objectives & hypotheses to be tested

Evaluate the acceptability, feasibility, and fidelity of current Vivo prototype in sedentary older adults with prediabetes

1: Assess a) attendance, benefits and barriers/facilitators of participation; b) ease of use; and c) overall satisfaction.

2: Assess trainer fidelity.

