Social Support	Perceived social support: "The people I spend most of my time with now encourage me in physical fitness activities" using a rating scale 1: strongly disagree and 5: strongly agree  Social Support within Vivo: "I have received support and encouragement from other [Vivo] participants to continue participating in this program?" 5-point scale of agreement
Self-efficacy	Five item question to determine beliefs in capability when faced with potential barriers, "Over the next three months, I am confident I can attend Vivo when ... (I am tired, in a bad mood, feel I don't have time, am on vacation, it's raining or snowing) with a 7-point scale of agreement 
Psychosocial Functioning	

Quality of Life; Mood; Depression; Stress, and satisfaction with life

Short Form Health Survey 36 (SF-36), Profile of mood state (POMS), Center for Epidemiologic Studies Depression Scale (CES-D), Perceived Stress Scale (PSS), Satisfaction with Life (SWL)

Each participant will receive a welcome kit that includes resistance bands to use during class along with written instructions about the assessments, and a tape measure.

Each cohort will meet virtually twice a week with their small group and certified trainer for 45 minutes.

All participants will complete a pre- and post-intervention virtual physical function assessment, 3-day food record, height, weight, waist circumference, and social support, self-efficacy, and psychosocial functioning questionnaires.

At 12-weeks, semi-structured interviews will be conducted to assess acceptability, usability and satisfaction.

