## Subject Recruitment and Compensation

- Describe recruitment procedures, including who will introduce the study to potential subjects. Describe how you will ensure that subject selection is equitable and all relevant demographic groups have access to study participation (per 45 CFR 46.111(a) (3)). Include information about approximately how many DUHS subjects will be recruited. If subjects are to be compensated, provide specific prorated amounts to be provided for expenses such as travel and/or lost wages, and/or for inducement to participate.

Participants will be recruited from outpatient Geriatrics, Endocrinology and Primary Care clinics serving Duke Health using Duke Office of Clinical Research, Research Innovation Center, Maestro Care recruitment tool, and from the Duke Health and Exercise Research Registry.

We will use the Duke Office of Clinical Research, Research Innovation Center, Maestro Care recruitment tool to identify potentially eligible patients in Duke Health geriatric medicine, endocrinology and primary care clinics. Using the Maestro Care electronic medical record, we will identify and invite older patients with prediabetes to be a part of our study. For any subject for which the study team and associates

do not have an established prior relationship, the patient's research contact preference will be noted and no contact will be made with those individuals with an opt-out status. Finally, we will check against the "banner" in MaestroCare to verify whether or not the patient has opted out for being contacted.

Clinicians in the geriatric medicine and primary care clinics may also refer potential subjects.

In addition, we will use the Duke Health and Exercise Research Registry.

The Duke Health and Exercise Research Registry was developed in April 2019 and is a registry of persons interested in exercise-related research studies. There are 4035 persons registered with a signed consent, contact information, and health information available for screening. Of these 4035, there are 600+ individuals who are  $\geq 60$  years; there are an additional 716 individuals with missing age, that would be included on the study invitation list, which would include over 1000 person's total.

We will recruit 30 sedentary adult men and women ages  $\geq 60$  including  $\sim 30\%$  non-white participants.

Participants will receive \$30 after the initial assessment and another \$50 after the endpoint assessment and semi-structured interview.

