### Data Analysis & Statistical Considerations

- Describe endpoints and power calculations. Provide a detailed description of how study data will be analyzed, including statistical methods used, and how ineligible subjects will be handled and which subjects will be included for analysis. Include planned sample size justification. Provide estimated time to target accrual and accrual rate. Describe interim analysis including plans to stop accrual during monitoring. Phase I studies, include dose escalation schema and criteria for dose escalation with definition of MTD and DLT.

A) Qualitative - To explore concepts related to a complex process (barriers, acceptability, and retention of a health behavior) the team will employ a qualitative analytical approach. Drs. [name] and [name] will use applied thematic analysis, organizing the data in response to the a priori questions contained in the semi-structured interviews and interview guides. Audio recordings will be transcribed verbatim following a transcription protocol. [name] and [name] will use NVivo 12 software to develop and apply structural (a priori) codes to segment participants' narratives into conceptual categories (e.g., all text describing a similar concept, such as psychosocial factors). Next, analysts will identify and apply content-driven (emergent) codes to the text for each of the conceptual categories (e.g., potential themes related to psychosocial factors). Inter-coder reliability assessments will be conducted on approximately 25% of transcripts during both structural and content coding. Discrepancies in coding will be resolved through analyst discussions; transcripts will be re-coded, and the codebook revised accordingly. Once coding is complete, we will examine code frequencies across transcripts to identify salient factors for each interview, followed by comparing and contrasting factors between interviews. The team will complete analytical memos describing the factors influencing success in adherence, usefulness and impact of Vivo on function and QOL, together with illustrative quotes for each.

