B) Quantitative - In this single-arm feasibility study with pre- and post-assessment (baseline and 12 weeks) we will use descriptive statistics to summarize the distribution of the covariates and dependent variables, and student t-tests to compare pre- and post-outcomes. These analyses are designed to support the feasibility of executing the fully powered randomized trial in Phase II. Primary outcome will be number of full stands that can be completed in 30 seconds with arms folded across chest. The 30-second has excellent test-retest reliability ( $r = 0.89$ , 95% CI = 0.79-0.93) and criterion validity compared to weight adjusted leg press ( $r = 0.77$ , 95% CI = 0.64-0.85). Additional outcomes include Balance component of the SPPB; 2-minute step test for aerobic endurance; 8-ft Timed Up and Go; 3-day food records; Waist Circumference; Perceived social support and Self-efficacy; Quality of Life Short Form Health Survey 36 (SF-36); Profile of mood state (POMS); Center for Epidemiologic Studies Depression Scale (CES-D); Perceived Stress Scale (PSS); Satisfaction with Life scale (SWL).

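### The only interview is at week 12 and is paid jointly with the endpoint assessment, with no provision for people who stop early, so reasons for leaving are likely to be under-counted

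*Combined protocol and SAP*

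**What the plan says.** **Objective.** The primary objective is to "Evaluate the acceptability, feasibility, and fidelity of current Vivo prototype in sedentary older adults with prediabetes" (State your primary study objectives). Purpose of the Study breaks this down as "Assess a) attendance, benefits and barriers/facilitators of participation; b) ease of use; and c) overall satisfaction", with trainer fidelity as a second item. That section does not itself mention interviews.

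**Interview.** Design & Procedures states: "At 12-weeks, semi-structured interviews will be conducted to assess acceptability, usability and satisfaction". The Research Abstract gives the same single time point and ties the qualitative interviews to barriers, acceptability and retention. The sentence on interviews names no population. The sentence on assessments, just before it, does: "All participants will complete a pre- and post-intervention virtual physical function assessment".

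**Payment.** Subject Recruitment and Compensation pays $30 after the initial assessment and a further $50 "after the endpoint assessment and semi-structured interview". The entry under Other Subject Compensation repeats this. No amount is attached to the interview by itself.

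**Analysis.** The qualitative part of Data Analysis & Statistical Considerations is meant "To explore concepts related to a complex process (barriers, acceptability, and retention of a health behavior"). The method is applied thematic analysis: structural and emergent codes, code frequencies across transcripts, comparison between interviews, and memos on what influences adherence. The quantitative part adds: "Primary outcome will be number of full stands that can be completed in 30 seconds with arms folded across chest".

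**Stopping.** The consent section lets participants stop whenever they wish. The text describes no exit interview, no contact at the time of stopping and no population for the interview analysis.

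**The concern.** A study of barriers and retention learns most from the people who met the barriers and did not stay. A single interview at the end of the programme, paid jointly with the endpoint assessment, is poorly placed to reach them.

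The gap matters because the outcome table under Design & Procedures lists no questionnaire on acceptability of, or satisfaction with, the programme. The Satisfaction with Life scale measures something else, and the programme-specific items cover peer support and confidence in attending. On the text available, the interview is the only stated instrument for acceptability and satisfaction. Attendance and retention counts will show who left and when, but not why.

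The study is meant to prepare a randomized trial in Phase II, which will need the reasons for leaving. Accounts not taken at the time cannot be reliably recovered afterwards.

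**Working it through.** **1. No planned figure to reproduce.** The documents state no dropout rate, no expected acceptability, no threshold and no acceptability proportion to be estimated. The check is therefore mainly a reading of the plan, with an illustration on declared assumptions.

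**2. Following the plan for one early stopper.** Suppose a participant stops in week 3.
- Timing: the only interview is at week 12, so at best the person is asked 12 − 3 = 9 weeks after stopping.
- Payment: the $50 follows the endpoint assessment and the interview together. Someone willing to talk but not to repeat the function tests has no stated payment.
- Analysis: nothing says whether this person's interview would be sought, or how its absence would be reported.

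**3. Effect on the analysis actually planned.** Code frequencies across transcripts identify the salient factors. Assume 6 of 30 enrolled stop early. A reason held only by early stoppers could appear in up to 6 of 30 transcripts (20%) if all are interviewed, and in 0 of 24 if none of the six is. A comparison between interviews also needs some from people who did not adhere.

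**4. Illustration on a percentage scale.** Let d be the share not interviewed, pc the share of those interviewed who find the programme acceptable, and pd the same share among those not interviewed.

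- All-enrolled share = (1 − d) × pc + d × pd
- Overstatement = d × (pc − pd)

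All three inputs are assumptions. With 30 enrolled (Design & Procedures) and pc = 0.90, the all-enrolled share, with the overstatement in points in brackets, is:

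| Not interviewed | pd = 0.90 | pd = 0.60 | pd = 0.30 | pd = 0 |
|---|---|---|---|---|
| 3 (10%) | 0.90 (0) | 0.87 (3) | 0.84 (6) | 0.81 (9) |
| 6 (20%) | 0.90 (0) | 0.84 (6) | 0.78 (12) | 0.72 (18) |
| 9 (30%) | 0.90 (0) | 0.81 (9) | 0.72 (18) | 0.63 (27) |

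Example: with 6 missed and pd = 0.30, 0.8 × 0.90 + 0.2 × 0.30 = 0.78, and 0.90 − 0.78 = 0.12.

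The Research Abstract gives 24 enrolled instead of 30, a conflict to be reconciled separately. With 24, missing 2, 5 or 7 people gives at most 7.5, 18.8 or 26.3 points, so the picture is similar.

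**5. What the illustration cannot show.** If nothing is assumed about those missed, the all-enrolled share at 20% missed lies between 0.8 × 0.90 = 0.72 and 0.72 + 0.20 = 0.92. That range includes 0.90, so arithmetic alone does not fix the direction. The expectation that leavers are less favourable is a judgement.

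**The case against.** The strongest reply is that the plan fixes a time, not a population. Week 12 can be read as calendar time since enrolment, all contact is virtual, and the neighbouring sentence asks for post-intervention assessments from all participants. A person who left in week 3 could still be interviewed in week 12. The interview guides are not among the documents and the consent pages were removed, so either may cover contact after stopping. The named primary outcome is the chair stand, and attendance, adherence and retention can be measured without an interview.

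Much of this stands, and it rules out a stronger reading. A reader might infer that interviews are restricted to completers and that the acceptability result is therefore biased upward by a calculable amount. The documents do not support that. No section limits interviews to completers. Upward bias needs some early stopping, failure to interview those people, and less favourable views among them, none of which the documents establish. People may leave because of illness or scheduling and still like the programme. The plan also produces no acceptability percentage to be biased.

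The reply does not remove the gap. Even on the calendar reading, the interview comes weeks after the event, and no payment is stated for it unless the endpoint assessment is also done. The chair stand being the named primary outcome does not change the stated primary objective, for which the interview is the only listed source on acceptability and satisfaction.

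**Conclusion.** The concern holds as a design weakness that should be corrected, not as a demonstrated bias. The likely harm is thin coverage of barrier and dropout themes and a favourable lean in the acceptability findings. Its size is unknown. The 0 to 27 points tabulated for 30 enrolled depend on assumed non-interview rates of 10% to 30%, an assumed 90% acceptability among those interviewed, and acceptability among those missed anywhere from 90% down to zero. The effect vanishes if nobody is missed or if leavers think as completers do, and it would reverse if leavers were more favourable. The part of the objective exposed is acceptability, satisfaction and barriers; attendance, retention, trainer fidelity and the chair stand do not rest on the interview.

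**What to change.** 1. **Design & Procedures (and the Research Abstract):** offer the interview to every enrolled participant, at week 12 for those still attending and soon after the last class attended for those who stop early, whether or not they do the endpoint assessment. State the window; about two weeks would be reasonable, but the choice is the study team's.
2. **Subject Recruitment and Compensation, and Other Subject Compensation:** make a stated part of the existing $50 payable for the interview alone. The total per person stays at $30 + $50 = $80.
3. **Data Analysis & Statistical Considerations, qualitative part:** report the number interviewed out of all enrolled, by completion status, and present barrier and acceptability themes separately for completers and early stoppers.

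The cost is a small wording change for the IRB and earlier scheduling of a few interviews. Some early stoppers will refuse, which the reported counts will make visible, and the acceptability findings may turn out less favourable.

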## Selection of Subjects

- List inclusion/exclusion criteria and how subjects will be identified.

### Inclusion Criteria

- Age  $\geq$  60 years;
- Diagnosis of Pre-diabetes within prior 12 months: fasting glucose between 100 to 126 OR HbA1c between 5.7 and 6.4%
- Ambulatory and community-dwelling
- Sedentary: less than 150 minutes of moderate physical activity OR less than 60 minutes of vigorous physical activity per week
- Have not engaged in resistance training for at least 6 months prior to enrollment
- Low functioning (defined as able to do at least 1 chair stand without using hand in 30 second but unable to meet the moderate function criteria for age and gender)
- Access to WiFi in defined exercise space
- Willing to maintain weight and current diet throughout the study

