## Design & Procedures

- Describe the study, providing detail regarding the study intervention (drug, device, physical procedures, manipulation of the subject or the subject's environment, etc.). Discuss justifications for placebo control, discontinuation or delay of standard therapies, and washout periods if applicable. Identify procedures, tests and interventions performed exclusively for research purposes or more

frequently than standard of care. Include alternative therapies, concurrent therapies discontinued per protocol, risk benefit ratio, and use of tissue/specimens. Discuss monitoring during washout periods if applicable. Include brief description of follow-up, if any.

This will be a 12-week single arm feasibility study using the currently available Vivo prototype to assess 1) adherence and retention, 2) acceptability and satisfaction with Vivo, 3) technology useability (i.e., Zoom, email), and 4) change in physical function in sedentary older adults with prediabetes and lower function.

**Remote Consent:** The study informational session is done one-on-one via a scheduled ZOOM meeting appointment with study staff. The secured REDCap platform will be used to obtain the participants' electronic consent (eConsent).

After informed consent and baseline assessments, 30 individuals will be enrolled in cohorts of 5-6 people.

Physical Function, Activity, and Diet Outcomes (baseline and week 12)	
Physical measurements	Height, weight, and waist circumference
30-second chair stands to quantify lower body strength	Number of full stands that can be completed in 30 seconds with arms folded across chest
Short Physical Performance Battery to quantify balance, lower extremity strength	Balance (side-by-side, semi-tandem, tandem), strength (time to complete 5 chair stands).
Gait speed tests	Number of seconds required to walk 4 meters
2-minute step test to measure aerobic endurance	Number of full steps completed in 2 minutes, raising each knee to a point midway between the patella (kneecap) and iliac crest (top hip bone)
8-ft Up and Go to assess agility/dynamic balance	Number of seconds required to get up from a seated position, walk 8 feet (2.44 m), turn, and return to seated position
30-second arm curl to quantify upper body strength	Number of arm curls completed in 30 seconds
Social Support and Self-efficacy	

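### The sedentary criterion joins its two activity limits with OR, so it excludes only people who reach both and admits some very active ones

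*Combined protocol and SAP*

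**What the plan says.** The Inclusion Criteria give one definition of the activity requirement: "Sedentary: less than 150 minutes of moderate physical activity OR less than 60 minutes of vigorous physical activity per week". It is the only place where the term is given a numerical meaning.

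The same list joins the two laboratory routes to a prediabetes diagnosis with the same capitalised word: "fasting glucose between 100 to 126 OR HbA1c between 5.7 and 6.4" (HbA1c in percent). There it plainly means that either test suffices.

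Two neighbouring criteria bear on fitness. Candidates must have done no resistance training for six months, and must be low functioning on the chair stand, that is, able to do at least one stand but "unable to meet the moderate function criteria for age and gender". The Exclusion Criteria contain no limit on physical activity.

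The population is named consistently elsewhere. The primary objective is to "Evaluate the acceptability, feasibility, and fidelity of current Vivo prototype in sedentary older adults with prediabetes". Design & Procedures lists among its aims "change in physical function in sedentary older adults with prediabetes and lower function". The recruitment section says "We will recruit 30 sedentary adult men and women ages" 60 or over. The abstract uses the same term.

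**The concern.** Two upper limits joined by OR make a very permissive rule: missing either one is enough. A person far above the moderate limit who does no vigorous exercise meets the vigorous half of the test (0 is below 60) and is therefore sedentary by definition. The mirror case, a great deal of vigorous activity and little moderate, also passes.

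At stake is whether the people enrolled are the people in the objective. Attendance, barriers, ease of use and satisfaction are to be learned in sedentary adults and carried forward to a randomized Phase II trial. If habitually active people are admitted, those findings describe a different group. One recruitment source is a registry of people interested in exercise research. That does not show its members are active, but it is a reason to want a criterion that works.

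The problem might also go unseen. The outcome list in Data Analysis & Statistical Considerations ("Additional outcomes include Balance component of the SPPB; 2-minute step test for aerobic endurance", and so on) contains no measure of weekly activity. The phone screen records exercise history, but the document does not say that minutes are captured or will be reported.

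**Working it through.** The plan gives no figure to reproduce here; the check is of the rule's logic.

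**Inputs.** Moderate limit 150 min/week and vigorous limit 60 min/week, joined by OR (Inclusion Criteria). Let M and V be a person's weekly moderate and vigorous minutes.

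**Step 1: who is excluded.** As written, eligible if M < 150 or V < 60. The negation is: excluded only if M ≥ 150 **and** V ≥ 60. If the limits were joined by AND, a person would be excluded on reaching either one.

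**Step 2: examples.**

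| M | V | As written (OR) | With AND |
|---|---|---|---|
| 0 | 0 | eligible | eligible |
| 149 | 59 | eligible | eligible |
| 300 | 0 | eligible | excluded |
| 600 | 0 | eligible | excluded |
| 600 | 59 | eligible | excluded |
| 0 | 300 | eligible | excluded |
| 150 | 60 | excluded | excluded |
| 300 | 120 | excluded | excluded |

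600 + 0 is 600/150 = 4 times the moderate limit; 0 + 300 is 300/60 = 5 times the vigorous limit. Both qualify.

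**Step 3: full enumeration.** For M = 0 to 600 and V = 0 to 300 in whole minutes there are 601 × 301 = 180,901 combinations.

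- Excluded as written: 451 × 241 = 108,691, and these are exactly the points with M ≥ 150 and V ≥ 60.
- Eligible with AND: 150 × 60 = 9,000, so 171,901 are excluded.
- Eligible as written but not with AND: 171,901 − 108,691 = 63,210.

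These counts confirm the logic. They do not estimate how many real candidates are affected.

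**Step 4: ordering.** The rule excludes 150 + 60 but admits 600 + 59. The second person does 450 more moderate minutes and one fewer vigorous minute. The ordering could be right only if one vigorous minute were worth more than 450 moderate ones.

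**Step 5: what AND leaves open.** The protocol does not combine the two limits. If their ratio is taken as an exchange rate (150/60 = 2.5, my assumption), an index M/150 + V/60 puts the most active person admitted under AND at 149/150 + 59/60 = 1.98, or 149 + 2.5 × 59 = 296.5 moderate-equivalent minutes. Under OR the index has no upper bound: 600 + 59 gives 4.00 + 0.98 = 4.98.

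**Step 6: do other criteria close the gap?** The resistance-training criterion does not concern aerobic activity, and the function criterion is defined by chair stands. A regular walker with a low chair-stand count and no resistance training meets both.

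**The case against.** The strongest reply is that the intent is obvious. The bullet opens with the label, the rest of the document repeats it, and a screener would have to ignore it to admit someone doing 600 minutes a week. The phone screen that applies the rule is an attachment we cannot see and may already use the stricter reading. This is also a 12-week single-arm feasibility study of resistance training whose stated primary outcome is chair stands. The criteria closest to that intervention and outcome, no recent resistance training and low chair-stand function, are in place and probably keep many active people out. No stated number changes, and no effect on results can be shown.

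Most of this stands as a limit on weight. The intended meaning probably is that neither limit is reached, and actual practice is unknown. It does not rescue the wording: the same list uses OR to mean that either condition suffices, no sentence says how the activity limits combine, and the neighbouring criteria do not cap aerobic minutes.

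Two supporting arguments deserve little weight. The outcome table is headed "Physical Function, Activity, and Diet Outcomes (baseline and week 12") but shows no activity row; it shows no diet row either, although a food record is planned, so rows may have been lost in text extraction. And a combined moderate/vigorous limit is a preference: admitting 149 + 59 contradicts nothing in the plan.

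**Conclusion.** The concern holds for the text. As written, the criterion excludes only people who reach both limits, sets no upper bound on activity as long as one limit is missed, and can admit a more active person while excluding a less active one. That conflicts with the sedentary population named in the abstract, objective, design and recruitment sections. It is an operative eligibility rule that gives the wrong result if followed, so it should be corrected. It does not invalidate the trial.

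The logic rests on no assumption beyond reading OR as the same list uses it for prediabetes. Its practical size is unknown: the document gives no activity distribution, so neither the share of affected candidates nor the direction of any effect on attendance or acceptability can be computed. No sample size or other stated figure changes.

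**What to change.** Replace OR with AND in the criterion, so that a participant must be below 150 moderate minutes and also below 60 vigorous minutes a week. If the investigators also want to exclude people just under both limits, a single combined limit (M/150 + V/60 below 1) would do so, but the defect is cured without it. Make the phone screen match, record both minute counts there, and report them in the baseline table so readers can see how sedentary the sample was.

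The edit is one word plus a phone-screen item. If staff already apply the stricter reading, recruitment is unaffected. If they do not, the pool shrinks, possibly substantially. As an illustration only: let a share pM of candidates reach the moderate limit and pV the vigorous limit, independently. The proportion of those admitted under OR who are lost under AND is 1 − (1 − pM)(1 − pV)/(1 − pM·pV).

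- pM = 0.30, pV = 0.05: 1 − 0.665/0.985 = 32%
- pM = 0.50, pV = 0.15: 1 − 0.425/0.925 = 54%
- pM = 0.70, pV = 0.30: 1 − 0.21/0.79 = 73%

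These shares are assumed, and they ignore selection on low function, so they do not describe this trial's actual pool. For scale, the target of 30 is 30/600 = 5.0% of the registry members known to be 60 or over, counted before the prediabetes, function and medication criteria; clinic recruitment adds to that source.
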